4.1 Primary Objective

To assess real world performance of the FDA cleared/CE marked Trevo Retriever intended to restore blood flow in the neurovasculature by removing thrombus in patients experiencing ischemic stroke.

5 Registry Endpoints

Clinical data will be evaluated in all subjects where the Trevo Retriever is used as the initial thrombectomy device to remove thrombus from the neurovasculature in the setting of acute ischemic stroke.

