6.1 Method of Enrollment

Clinical data points will be evaluated in all subjects who meet the inclusion/exclusion criteria and where Trevo Retriever is used as the initial mechanical thrombectomy device to remove thrombus from the neurovasculature in the setting of acute ischemic stroke. For purposes of this registry, enrollment occurs when the Trevo Retriever is deployed through the compatible Microcatheter into the neurovasculature as the first mechanical neuro-thrombectomy device used to remove the thrombus.

A Screening and Enrollment Log will be maintained by each site to document basic information such as date screened and reason for screen failures for subjects who fail to meet the study eligibility criteria. In order to avoid bias, if a center chooses to participate in the Trevo Registry, every effort should be made to include all Trevo cases performed over a given duration of time in the registry. No site will be allowed to enroll more than 15% (300 subjects) of the entire maximum study population unless first approved by Stryker.

7 Study Population

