7.1 Selection Criteria

7.1.1 Inclusion Criteria:

1. Subjects experiencing acute ischemic stroke who are eligible for restoration of blood flow using a Trevo Retriever in the neurovasculature to remove thrombus
2. Trevo Retriever is the initial mechanical neuro-thrombectomy device used to remove the thrombus
3. Signed Informed Consent obtained
4. Subject willing to comply with the protocol follow-up requirements
5. Anticipated life expectancy of at least 3 months

Trevo[®] Retriever Registry

7.1.2 Exclusion Criteria:

The subject is participating in another mechanical neuro-thrombectomy device trial or any other clinical trial where the study procedure or treatment might confound the study end point.

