8.1 Written Informed Consent

A sample ICF is provided in **Appendix C** for the Investigator to prepare for use at the site. The written Informed Consent documents must be prepared in the language(s) of the potential subject population. The ICF must be approved by the study Institutional Review Board (IRB)/Ethics Committee (EC) and a copy provided to Stryker Neurovascular. Modifications to the form must be approved by Stryker Neurovascular prior to implementation. The document version must be identified on the ICF to maintain version control.

Written Informed Consent must be obtained for all subjects prior to data entry into the Trevo Retriever Registry electronic database. The subject or the subject's legally authorized representative (LAR) will be asked to sign the ICF. Consent should be obtained pre-procedure but depending on subject's acuity the consent may be obtained up to seven days post-procedure. No data may be entered into the database until written consent has been obtained. In the absence of informed consent, an IRB/EC approved waiver of consent and executed data use agreement must be in place.

Study personnel should document the consent process in the subject's medical record per Good Clinical Practice (GCP). The subject or LAR is to be provided a copy of the signed ICF.

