9.2 Analysis Populations

The Intent-to-treat principle will be followed to define the analysis population. All of the subjects who signed the informed consent and in whom Trevo Retriever was deployed through the microcatheter are considered enrolled and will be included in the analyses.

Sub-group analyses for the Registry will be performed under guidance from the Study PIs, Steering Committee, and Sponsor.

Day 90 outcomes will be compared to pre-stroke mRS status, baseline imaging and time of symptom onset to treatment. The first interim analysis will be performed after 300 subjects are enrolled and the results will be reported. Additional interim analyses and data reporting will occur throughout the study enrollment period.

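### The signed-consent rule in 9.2, criterion 3 and Appendix D leaves out the waiver cases that 8.1 accepts, and consent after the procedure makes analysis membership depend partly on early survival

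*Protocol*

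**What the plan says.** Protocol 9.2 names the intent-to-treat principle and then fixes who is analysed: "All of the subjects who signed the informed consent and in whom Trevo Retriever was deployed through the microcatheter are considered enrolled". Inclusion criterion 3 in 7.1.1, repeated in the synopsis, reads "Signed Informed Consent obtained". A footnote to the Appendix D schedule requires written consent before any data entry. None of these three places mentions a waiver.

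Section 8.1 prefers consent before the procedure but, depending on acuity, "the consent may be obtained up to seven days post-procedure". The subject may sign, or a "legally authorized representative (LAR) will be asked to sign the ICF". Until then, "No data may be entered into the database until written consent has been obtained". The next sentence opens another route: "In the absence of informed consent, an IRB/EC approved waiver of consent and executed data use agreement must be in place".

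Section 6.1 uses a different event: "enrollment occurs when the Trevo Retriever is deployed through the compatible Microcatheter into the neurovasculature", with no mention of a signature. It also asks sites, in order to avoid bias, to try to bring in every Trevo case treated over a given period. Section 5 says "Clinical data will be evaluated in all subjects where the Trevo Retriever is used as the initial thrombectomy device to remove thrombus", and 6.1 repeats that statement with the condition that subjects meet the inclusion and exclusion criteria.

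**The concern.** Two things do not fit together.

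First, 8.1 admits a class of subjects, those under a waiver with a data use agreement, that 9.2 and criterion 3 do not recognise. A site following 8.1 and a statistician following 9.2 could reach different denominators from the same protocol.

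Second, enrollment happens at deployment in one section and needs a signature in another, and the signature may come up to a week later. Whether a treated subject is analysed can then depend on someone signing before the subject dies. By itself, losing unsigned early deaths lowers reported Day 90 mortality and raises the share with mRS 0-2, both secondary endpoints. Surviving subjects who never sign push mortality the other way.

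**Working it through.** **Comparing the rules.**

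| Place | Condition | Waiver mentioned? |
|---|---|---|
| 6.1, enrollment event | Trevo deployed as first device | No |
| 7.1.1, criterion 3 | Signed consent | No |
| 8.1 | Written consent, up to 7 days after the procedure, by subject or representative; or waiver plus data use agreement | Yes |
| 9.2, analysis set | Signed consent and Trevo deployed | No |
| Appendix D footnote | Written consent before data entry | No |

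A waiver case satisfies 6.1 and 8.1 and fails criterion 3 and 9.2. A subject who dies unsigned with no waiver satisfies 6.1 but cannot be entered under 8.1, although 8.4 expects deaths before the 24-hour assessment to be recorded.

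**How large could the effect be?** The protocol has no figure to reproduce. The following is an illustration on assumed inputs.

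- True Day 90 mortality m: 33% (29/88, Trevo arm of TREVO 2, Table 4) or 20% (12/60, TREVO, Table 1).
- True mRS 0-2 share g: 40% (34/85, TREVO 2) or 55% (33/60, TREVO).
- Share of treated cases lost, l: assumed 1% to 4%; not in the documents.
- Death share among lost cases, q: not in the documents; taken as 1, 2m, m and 0.

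Observed mortality = (m − l·q)/(1 − l). For example, m = 0.33, q = 1, l = 0.04 gives 0.29/0.96 = 30.2%. Results for l = 1% to 4%:

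| True m | q = 1 | q = 2m | q = m | q = 0 |
|---|---|---|---|---|
| 33% | 32.3% to 30.2% | 32.7% to 31.6% | 33.0% | 33.3% to 34.4% |
| 20% | 19.2% to 16.7% | 19.8% to 19.2% | 20.0% | 20.2% to 20.8% |

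The 95% half-width at n = 2000 is 1.96·√(m(1 − m)/2000), or 2.06 points at 33% and 1.75 points at 20%.

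The shift equals the half-width when l/(1 − l) = k, with k = half-width/(q − m), so l = k/(1 + k):

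- q = 1: k = 0.0206/0.67 gives l = 3.0%, and k = 0.0175/0.80 gives l = 2.1%. Beside 2000 entered subjects these are about 62 and 44 lost cases.
- q = 2m: l = 5.9% and 8.1%, both outside the assumed range.

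For mRS 0-2, if no lost case had a good outcome, observed share = g/(1 − l). Then 40% reads 40.4% to 41.7%, and 55% reads 55.6% to 57.3%. The half-widths are 2.15 and 2.18 points, reached at l = 5.1% and 3.8%.

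The one early-death figure in the protocol is 24-hour mortality of 2/88 in the Trevo arm of TREVO 2 (Table 3). Dropping both deaths turns 29/88 = 33.0% into 27/86 = 31.4%, a shift of 1.6 points, below the 2.06-point half-width at n = 2000. No seven-day figure is given.

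**The case against.** The strongest reply is that this is a wording gap. Section 9.2 says who is included and does not say that waiver cases are discarded; 8.1 is the specific provision and could be taken to govern. That is fair for 9.2. It does not dispose of criterion 3, an eligibility condition with no exception.

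A reader might also infer that section 5 contradicts 9.2 outright because it speaks of all subjects. The protocol does not support that: 6.1 restates the sentence subject to the inclusion and exclusion criteria, which include consent.

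On early deaths, consent before the procedure is the default, a representative may sign, and a waiver may apply. Only cases with none of these are lost. This reduces the loss without removing it.

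The log in 6.1 would already show a missing signature as a reason for screen failure. But what 6.1 specifies is basic information, such as screening date and reason. It does not call for marking that Trevo was deployed first or for vital status.

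Finally, use of log counts and bounds may sit in an SAP that is not shown. That is right, so their absence is not the finding; they are offered as part of the remedy. The finding is that the protocol states its analysis set in ways that cannot all be applied.

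**Conclusion.** The point holds as an inconsistency that should be fixed. Read literally, 9.2, criterion 3 and the Appendix D footnote leave out waiver cases that 8.1 accepts. The signature that 9.2 adds to the 6.1 enrollment event can come after treatment, so membership depends partly on post-treatment events. Confidence is high for this, because it rests on the text.

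A reader might go further and infer that the registry will materially understate mortality. The documents do not support that. Neither the share lost nor the deaths among those lost is given, and the net direction depends on whether unsigned cases die more often than entered ones. Within the assumed 1% to 4% loss, the shift exceeds sampling error at n = 2000 only in extreme cases: every lost case dead and more than 3.0% lost (at 33% mortality) or 2.1% lost (at 20%), or no good outcome among lost cases and more than 3.8% lost (at 55% mRS 0-2). The 2000 is a maximum; a smaller registry would have wider sampling error.

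**What to change.** In 9.2, define the analysis set as all otherwise eligible subjects with Trevo deployed as the first device who have signed consent (subject or representative) or are entered under an IRB/EC-approved waiver with a data use agreement. Align criterion 3 (including the synopsis), 6.1, 8.1 and the Appendix D footnote with it.

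This does not recover unsigned cases without a waiver; they stay outside the set. So have the Screening and Enrollment Log flag and count each Trevo-first case not entered, with the reason and, where permitted, vital status. Report that count L beside Day 90 mortality with the bound D/(N + L) to (D + L)/(N + L), where D is deaths among the N entered:

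- D = 660, N = 2000, L = 62: 660/2062 = 32.0% to 722/2062 = 35.0%, around a reported 33.0%.
- D = 400, N = 2000, L = 44: 400/2044 = 19.6% to 444/2044 = 21.7%, around a reported 20.0%.

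The bound straddles the reported rate, so it shows the possible range and does not settle direction. The reported rate is too low only if deaths among the lost exceed L·D/N: 62 × 0.33 = 20.5 in the first example and 44 × 0.20 = 8.8 in the second. Known vital status at Day 90 narrows the bound.

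The cost is protocol wording and two log columns. Some IRBs/ECs may refuse a waiver or vital status on the log; those outcomes then stay unknown and the bound stays wider.

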9.3 Statistical Analysis

All statistical analyses will be performed using SAS version 9.2 or above. (Copyright © 2002-2008 by SAS Institute Inc., Cary, North Carolina, USA, All rights reserved)

10 Data Management

10.1 Data Collection and Processing

Data will be collected in a secure, password protected electronic data capture (EDC) system, which is accessible via the Internet. All pertinent data will be entered by trained study center personnel into the electronic Case Report Forms (eCRFs). A unique subject ID number will be assigned to each subject. Every reasonable effort should be made to complete data entry within one week of data collection. Any data discrepancies may be queried during ongoing review of data by the sponsor or may be identified and queried during routine remote monitoring process. Remote monitoring may be performed to verify data accuracy and ensure queries are resolved. The Principal Investigator or Sub-investigator must ensure the accuracy and completeness of the recorded data and provide his/her electronic signature on the appropriate eCRF.

Trevo[®] Retriever Registry

If images are sent to a Core Lab the results may also be entered into the EDC system and may be electronically signed by the reviewer responsible for entering this data. Ongoing data review will be performed to identify possible data discrepancies. Manual and/or automatic queries will be created in the EDC system and will be issued to Core Lab for appropriate resolution.

11 Monitoring

Data will be monitored remotely for completeness and logical consistency. De-identified procedure summary, anesthesia record, Trevo Registry worksheets and UB-04 forms or equivalent claims forms per country must have the Trevo Registry subject identification number recorded on any forms sent to Stryker Neurovascular. The de-identified procedure documents may be compared against the eCRFs to ensure consistency for each subject enrolled.

Stryker Neurovascular will conduct an assessment of each participating site to assure that the investigators understand the investigational plan, as well as, their obligations to conduct the registry in accordance with applicable Regulations, GCP's and the registry protocol. The monitor will also confirm that the investigator has an adequate subject population, facilities, personnel and time to conduct the registry properly. Periodic monitoring visits may be made to confirm that the site remains compliant with the protocol, applicable Regulations, GCP and that all agreed-upon activities are carried out by the investigator and other specified staff members.

It is important that the Investigator and relevant study site personnel are available during monitoring visits and that sufficient time is devoted to the process. In order to perform her or his role well, the monitor must be given access to primary subject medical records which support the registry eCRFs. This access must be disclosed to the subject via the informed consent.

The investigator agrees to complete all registry requirements within three months of written notice of enrollment completion. Continuation of the registry beyond this time must be mutually agreed upon in writing by both the investigator and Stryker Neurovascular.

Stryker Neurovascular will conduct a registry closeout meeting with each Trevo Registry site after the final data query is generated and data requests are addressed. The purpose of the closeout meeting is to confirm that all registry-related activities are complete and site personnel are aware of the regulatory obligations following study closure activities. The closeout meeting may transpire remotely e.g. teleconference or at an on-site monitoring visit. The closeout activities include but are not limited to the following:

- Final regulatory document review and collection of any outstanding documents including a copy of the investigator notification letter sent to the IRB/EC regarding completion of the Trevo Retriever Registry
- Address and close any open action items
- Discuss record retention requirements
- Review publication guidelines

12 Auditing

Sites may be subject to a quality assurance audit by Stryker Neurovascular or its designees, or other regulatory authorities.

Trevo[®] Retriever Registry

It is important that the Investigator and relevant study personnel are available during any audits and that sufficient time is devoted to the process.

13 Device Accountability

There will be no device accountability or tracking as the Trevo Retriever has regulatory authorization to market the device.

14 Adverse Events

The following adverse events will be reported:

- all adverse events that occur during the procedure
- all SAEs related to the device or the procedure through Day 90
- all adverse events that result in death through Day 90

14.1 Adverse Event Definitions and Classification

Term	Definition	Reference
Adverse Event (AE)	Any untoward medical occurrence in a subject. This definition does not imply that there is a relationship between the adverse event and the device under investigation.	ISO 14155-1
Adverse Device Effect (ADE)	Any untoward and unintended response to a medical device. Note 1: This definition includes any event resulting from insufficiencies or inadequacies in the instructions for use or the deployment of the device. Note 2: This definition includes any event that is a result of a user error.	ISO 14155-1
Serious adverse event (SAE)	An adverse event that: 
• led to death• resulted in a life-threatening illness or injury• resulted in a permanent impairment of a body structure or a body function• required in-subject hospitalization or prolongation of existing hospitalization• resulted in medical or surgical intervention to prevent permanent impairment to body structure or a body function• led to fetal distress, fetal death or a congenital abnormality or birth defect	ISO 14155-1

STRYKER CONFIDENTIAL - THIS DOCUMENT CONTAINS CONFIDENTIAL AND PROPRIETARY INFORMATION THAT IS THE PROPERTY OF STRYKER CORPORATION. NEITHER THIS DOCUMENT NOR THE INFORMATION HEREIN MAY BE REPRODUCED, USED, OR DISCLOSED TO ANY THIRD PARTY WITHOUT THE PRIOR WRITTEN CONSENT OF STRYKER CORPORATION.

CDM 1000023 Rev. AC

Trevor[®] Retriever Registry

Term	Definition	Reference
Serious Adverse Device Effect (SADE)	An adverse device effect that has resulted in any of the consequences characteristic of a serious adverse event or that might have led to any of these consequences if suitable action had not been taken or if circumstances had been less fortunate.	ISO 14155-1
Unanticipated Adverse Device Effect (UADE)	Serious adverse device effect which by its nature, incidence, severity or outcome has not been identified in the current version of the risk analysis report	ISO 14155-1

Underlying diseases are not reported as AEs unless there is an increase in severity or frequency during the course of the registry. Death should not be recorded as an AE, but should be reflected as an outcome to a specific AE.

14.2 Relationship

The Investigator must assess the relationship of the AE to the study device using the following criteria categories and definitions:

Unrelated - The AE is due to a concurrent illness or effect of another device/drug and is not related to the study device.

Related - The AE is due to the study device (possible, probable, or highly probable).

Unknown - The temporal relationship between the AE and study device cannot be clearly determined.

The Investigator must assess the relationship of the AE to the index procedure using the following categories and definitions:

Unrelated - The AE is due to a concurrent illness or effect of a drug and is not related to the index procedure.

Related - The AE is due to the index procedure (possible, probable, or highly probable).

Unknown - The temporal relationship between the AE and index procedure cannot be clearly determined.

14.3 Reporting Requirements

All required AEs (i.e. all AEs resulting in deaths and device and procedure related AE) will be recorded in the appropriate eCRFs.

All required SAEs and UADEs shall be reported within 24 hours of becoming aware to Stryker Neurovascular via data entry into the eCRFs. If access to eCRFs is not available then the information can be faxed to the Stryker Neurovascular Safety Department personnel listed in current Study Contacts List provided in the study binder.

Trevo[®] Retriever Registry

14.4 Device Failures, Malfunctions, and Product Nonconformities

All Trevo Retriever failures, malfunctions, and product nonconformities will be documented on the appropriate eCRF and the involved device(s) should be returned to Stryker Neurovascular for analysis if possible. Instructions for returning the study device(s) will be provided to the sites in their study binder. Device failures and malfunctions should also be documented in the subject's medical record.

All Trevo Retriever failures, malfunctions, and product nonconformities shall be reported within 24 hours of becoming aware to Stryker Neurovascular via data entry into the eCRFs. If access to eCRFs is not available then the information can be faxed to the Stryker Neurovascular Safety Department personnel listed in the current Study Contacts List provided in the study binder.

NOTE: Trevo Retriever failures, malfunctions, and product nonconformities should be reported as soon as possible after becoming aware of them and are not to be reported as adverse events. However, if there is an adverse event that results from a device failure or malfunction, that specific event would be recorded on the appropriate eCRF. Trevo Retriever failures, malfunctions, product nonconformities and resulting AEs are reported to the Stryker Neurovascular complaint reporting system.

All Stryker Neurovascular non-study device malfunctions and nonconformities related to ancillary devices used in the procedure should be reported to the local Stryker Neurovascular customer service center. The customer service listing is provided in the study binder.

14.5 Reporting to Regulatory Authorities / IRBs / IECs / Investigators

Stryker Neurovascular is responsible for reporting adverse event information to all participating investigators and regulatory authorities, as applicable.

The Site PI is responsible for informing the IRB/ Independent Ethics Committee (IEC) of UADEs and SAEs as required by local procedure. A copy of this report should be sent to Stryker Neurovascular.

15 Risk Benefit Analysis

The risks associated with this study are limited to a possibility that confidential patient information may be disclosed. It is possible that subjects enrolled into the Trevo Registry will receive no direct benefit from participation. Possible benefits of the registry include providing information regarding the use of the Trevo Retriever that may benefit future patients.

15.1 Risk Minimization

In order to minimize risks, Stryker Neurovascular will carefully select study sites and investigators who have experience with neuro-interventional procedures. Thorough training on the protocol, IFU and registry requirements will be conducted and Stryker Neurovascular will be available to address any registry specific issues or questions. Reasonable measures will be taken to minimize any risk of loss of confidentiality including the use of subject ID numbers for data entry and de-identification of any images or records sent to the core-lab or Stryker. A Steering Committee will assist in oversight of the Trevo Registry and Safety monitoring of the data will be continuous throughout the registry.

Trevo[®] Retriever Registry

16 Steering Committee

The Trevo Retriever Registry will include a Steering Committee of up to 5 members or more of which one member may assume the Trevo Registry PI role. The Steering Committee will assist in oversight of the Trevo Registry with regard to protocol review and study progress. The Steering Committee will oversee dissemination of any study results through appropriate scientific sessions and publications. One of the Steering Committee members will Chair the publication committee. The Steering Committee will prepare a manuscript for publication of the interim analyses that will begin after 300 subjects have been enrolled. Subsequent interim analyses may be conducted and published throughout the study enrollment period. The Steering Committee may select study investigators to participate on the publication committee. These additional publication committee members are chosen based on enrollment, adherence to the protocol and protocol deviation rates. The Steering/ Publication Committee will participate in the review and approval of all requests for data analyses, abstract and manuscript preparation and submission.

17 Ethical Considerations

